3.9.2.1 Adverse Events of Special Interest (AESI)

Adverse events of special interest (AESI) are those that require special collection and/or reporting. They are not necessarily those expected to be related to study drug or those most frequently occurring.

The following adverse events have been identified as an important medical risk:

AESI	Definition
Ocular adverse events related to vitamin A deficiency	AE with HLT: Fat soluble vitamin deficiencies and disorders; or AE with PT: Vitamin A decreased; or AE with PT: Vitamin A abnormal; or AE within the SMQ: Optic nerve disorders; or AE within the SMQ: Corneal disorders; or AE within the SMQ: Retinal disorders
Thrombocytopenia	AE with HLT: Thrombocytopenias; or AE with HLT: Platelet analyses
Renal Impairment	AE within the SMQ: Acute renal failure

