ISIS 420915 was well-tolerated at the dose levels and dose regimens tested. There were no serious adverse events (SAE). Two (2) discontinuations were considered possibly related to ISIS 420915, 1 due to constitutional symptoms (400 mg subject) and 1 due to injection site reactions (300 mg subject). The main safety findings included mild injection site reactions characterized most often by pain and erythema. The duration of the reactions were typically 24 hours and resulted from some but not all injections. This injection site reaction profile is considered similar to the profile for other 2'-MOE ASOs. Transient C-reactive protein elevations, primarily associated with the first injection, were observed in nearly all treated subjects at 200 mg multiple-dose or higher. The peak elevations were generally observed 2 days after the first dose of ISIS 420915 (Study Day 3) and resolved within 2 weeks despite continued dosing. For those subjects with C-reactive protein > 10 mg/L, the peak values at Day 3 had a median of 36 mg/L (range from 14 to 169 mg/L). Retinol reductions below the lower limit of normal (LLN) occurred in approximately 50% of subjects treated in the multiple-dose cohorts. The minimum retinol value was 0.19 mg/L (range 0.05 to 0.27 mg/L). Recovery to above the LLN occurred approximately 1-month after the final dose of ISIS 420915. The retinol reduction was an expected consequence of TTR reduction.

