8.5.3 Safety Monitoring Rules for Ocular Effects

All patients should receive an ophthalmology examination by an eye specialist at Baseline, after approximately 7 months of receiving Study Drug (Week 29) and also at the end of the dosing period (Week 65). An ERG will also be performed at Baseline and the end of the dosing period (Week 65). In addition, any patient that complains of persistent ocular symptoms compatible with vitamin A deficiency (e.g., night blindness or dry eyes) should be referred for an ophthalmology examination. If the ophthalmologist confirms the patient's symptoms are consistent with vitamin A deficiency and/or the examination reveals physical findings that are consistent with vitamin A deficiency (but do not reach the stopping rule criteria described in Section 8.6.4) then an ERG examination should be conducted and analyzed by the central reader. In addition, it is suggested that a review of diet and supplement use and an evaluation for factors which may contribute to low vitamin A levels such as infection, alcohol consumption, and zinc and/or iron deficiency be conducted.

If the ERG is changed from baseline and shows clear signs of vitamin A deficiency as assessed by the central reader and described below, then the patient should be monitored more frequently. Frequency will be determined by the Sponsor Medical Monitor in consultation with the Investigator and ophthalmologist.

Clear signs of vitamin A deficiency as assessed by ERG include:

- a) Changes from baseline > 50%, and
- b) Values below normal range (if baseline values were within normal range), and
- c) Changes that are approximately symmetrical between eyes (unless there is an alternative explanation for asymmetry)

Dosing with Study Drug may continue while these evaluations are being performed.

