ISIS 420915-CS2 is a randomized, double-blind, placebo-controlled, multicenter study of approximately 15 months treatment duration and 6 months follow-up. Approximately 135 patients will be randomized in a 2:1 ratio (90 ISIS 420915 and 45 placebo) to receive 300 mg ISIS 420915 or placebo. Study Drug (ISIS 420915 or placebo) will be administered three times on alternate days during Week 1 (Days 1, 3 and 5), and then once weekly during Weeks 2–65 (for a total of 67 doses). The end-of-treatment (EOT) efficacy assessment is conducted at Week 66. Following treatment and the EOT efficacy assessment, eligible patients (including patients who received placebo) may elect to enroll in an open-label extension (OLE) study pending study approval by the IRB/IEC and the appropriate regulatory authority. All participating patients in the OLE study will receive 300 mg ISIS 420915 once weekly. Otherwise, patients will enter the 6 month post-treatment evaluation portion of the study.

Patients in the study will be Stage 1 (approximately 50%) and Stage 2 (approximately 50%) FAP patients with the following characteristics:

- a. Neuropathy impairment score (NIS) score ≥ 10 and ≤ 130
- b. Documented transthyretin variant by genotyping
- c. Documented amyloid deposition by biopsy

Interim safety data will be reviewed regularly by the ISIS 420915-CS2 DSMB.

A pharmacodynamic interim analysis of reduction in plasma TTR level will be performed by an independent statistician and reviewed by the DSMB after approximately 45 patients have completed the Week 13 visit. This interim will be a futility analysis and will result in a decision to continue the study as planned or to stop the study.

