Summaries of related TEAEs, TEAEs by maximum severity, TEAEs during the safety treatment period, and TEAEs grouped by time from first dose to event onset (< 6 months, ≥ 6 months to < 12 months, ≥ 12 months) will also be provided.

All TEAEs will be summarized for subgroups defined by the following variables: Age, Sex, Race, Region, CM-ECHO Set, V30M TTR mutation, previous treatment with Vyndaqel® or Diflunisal, disease stage. Results will not be provided for a variable if the overwhelming majority of patients are within one level of the subgroup. Non-TEAEs reported will be flagged in the all AE listing.

A listing will be provided stating which subjects reported each preferred term. Adverse events in the following categories will be summarized separately:

- Adverse events of special interest
- Other adverse events of interest

Summary tables of the number and percentage of subjects with these adverse events will be displayed split by AE category and treatment group. TEAEs of special interest and other TEAE of interest will also be summarized for patients in the CM-ECHO Set. Statistical comparison between treatment groups will be done for AEs of special interest and other AEs of interest using the risk difference (ISIS 420915 – Placebo) and associated 95% CI.

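### The vitamin A eye-safety AESI counts vitamin-deficiency and laboratory terms with no eye finding, so its planned risk difference is not a difference in ocular events

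*SAP*

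**What the plan says.** SAP 3.9.2.1 lists three AESIs. The first carries a label naming ocular events linked to vitamin A deficiency. Six alternative criteria define it. They open with "AE with HLT: Fat soluble vitamin deficiencies and disorders; or AE with PT: Vitamin A decreased" and go on to "AE with PT: Vitamin A abnormal; or AE within the SMQ: Optic nerve disorders"; the last two are the standardised queries (SMQs) for corneal and for retinal disorders. No criterion is conditional on another.

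SAP 3.9.2 gives these categories a between-arm analysis: "Statistical comparison between treatment groups will be done for AEs of special interest and other AEs of interest using the risk difference", with a 95% CI. The interval method is not named. The AESIs are also summarised in the CM-ECHO Set.

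Protocol 2.3.4 reports from Phase 1: "Retinol reductions below the lower limit of normal (LLN) occurred in approximately 50% of subjects treated in the multiple-dose cohorts". It adds: "The retinol reduction was an expected consequence of TTR reduction".

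**The concern.** A patient with an adverse event of low vitamin A, or of deficiency of another fat-soluble vitamin, and entirely normal eyes meets the definition and is tabulated as an ocular case. The row then mixes two questions: whether the eye is harmed, and whether vitamin status is altered. The second is partly expected pharmacology of the drug, so non-ocular cases are not guaranteed to fall evenly across the arms.

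The row matters because it is the only eye-safety output in SAP 3.9 with a specified between-arm interval. Under SAP 3.9.6, ERG change is summarised by arm, ophthalmology findings are listed, and discontinuations under the ocular stopping rule are tabulated. A reader who goes to the interval for the answer on eye harm would be reading an estimate of something else.

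**Working it through.** The plan states no event rate, power or expected count for this AESI, so there is no figure to reproduce. The check is of the definition, followed by the arithmetic of a single case.

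**Step 1: criteria against label.**

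| Criterion (SAP 3.9.2.1) | Eye finding required? | Limited to vitamin A? |
|---|---|---|
| HLT for fat-soluble vitamin deficiencies and disorders | No | No, by its name |
| PT Vitamin A decreased | No (laboratory term) | Yes |
| PT Vitamin A abnormal | No (laboratory term) | Yes |
| SMQ optic nerve disorders | Yes | No |
| SMQ corneal disorders | Yes | No |
| SMQ retinal disorders | Yes | No |

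As the criteria are alternatives, either of the first two answers in the middle column is enough to admit a non-ocular case.

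**Step 2: weight of one case.** Inputs: 90 patients on ISIS 420915 and 45 on placebo (SAP 1.1). Assume that the Safety Set has these sizes and that the patient does not also qualify through an eye SMQ.

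- One case on ISIS 420915: 1/90 = 1.1 points added to that arm and to the risk difference.
- One case on placebo: 1/45 = 2.2 points added to that arm and taken off the risk difference.

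So the contamination can push the row either way.

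**Step 3: scale only, with assumed counts.** Suppose no eye event occurs in either arm.

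- Eye terms alone: 0/90 vs 0/45, difference 0 (Newcombe 95% CI −7.9% to 4.1%).
- Present definition, 4/90 vitamin or laboratory cases vs 0/45: difference 4/90 = 4.4%. Wald SE = √(0.0444 × 0.9556 / 90) = 0.0217, so the CI is 4.4% ± 1.96 × 2.17% = 0.2% to 8.7%. With 3/90 the Wald interval still includes 0 (−0.4% to 7.0%).
- By Newcombe, 9/90 vs 0/45 is the first count to exclude 0: 10.0% (0.9% to 17.9%). With 8/90 it is −0.1% to 16.6%.
- With an equal background of 2/45 and 4/90, it takes 13/90 in total (9 extra) by Wald or 15/90 (11 extra) by Newcombe.

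These are thresholds, not forecasts. The Wald figure is fragile because an arm with no events contributes no variance. The gap between 4 and 9 shows that the unnamed interval method matters.

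**Step 4: equal background.** If a fraction *b* of both arms has an unrelated vitamin adverse event, independent of eye events, the row's difference is (1 − *b*) times the ocular difference. With *b* assumed at 2% to 5%, a true 10-point difference becomes 9.8 to 9.5 points.

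**The case against.** The strongest reply is that the route for inflation is mostly closed.

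- Protocol 4.4 withholds retinol values from the sponsor, monitors, investigators, site staff and patients. SAP 2.5.2 keeps post-treatment values withheld until the EOT lock and unblinding.
- Protocol 9.5.1 says that laboratory abnormalities judged not clinically significant should not be reported as adverse events, and prefers a diagnosis to a laboratory value.
- The schedule in Appendix A shows no separate local retinol testing.

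This stands. A reader might take the Phase 1 figure of about 50% below the lower limit of normal as the rate at which these terms will be reported. It is a laboratory rate, and the documents do not support that use. Vitamin-only cases would have to come from outside testing, a clinical diagnosis or the unblinding of a patient.

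Second, the components can be separated from other outputs. Adverse events are tabulated by SOC and PT and listed by PT (SAP 3.9.2), eye examinations are reported (SAP 3.9.6), and retinol and retinyl palmitate are summarised with the safety laboratory data (SAP 3.6). This also stands, so it would be wrong to infer that the plan cannot address eye harm. It does not correct the label or the planned interval.

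Third, broad categories are the SAP's habit: the thrombocytopenia AESI also combines a clinical HLT with a laboratory one. The parallel is imperfect. A platelet count is what that label names, whereas a vitamin level is not an eye event. The closer precedent is haemorrhage in SAP 3.9.2.2, where test results are separated from actual bleeds.

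Two further inferences rest on MedDRA content that the documents do not contain. One is that night blindness and dry eyes, named in Protocol 8.5.3, are missed; the eye SMQs may hold them. The other is that the whole HLT is non-ocular and can be dropped; it may include eye manifestations of vitamin A deficiency.

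**Conclusion.** The point holds as a defect of definition and labelling in a safety summary. Non-ocular vitamin and laboratory adverse events would be reported as ocular, and the row's risk difference and interval do not estimate an ocular difference. The size is 1.1 points per such case on ISIS 420915 and 2.2 on placebo, assuming the planned arm sizes. The number of cases cannot be derived from the documents, and the blinding of retinol and the reporting rule for laboratory findings limit it.

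A reader might conclude that the drug's retinol lowering will produce a false eye signal, or that background vitamin deficiency will hide a true one. The documents support neither. The first needs adverse event rates that are given nowhere, and the second is a small effect at the backgrounds assumed above. The breadth of the HLT is judged from its name alone. Primary efficacy is not touched.

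**What to change.** Before unblinding, amend SAP 3.9.2.1 as follows.

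- Keep the broad category under an accurate name, for example *Vitamin A deficiency and ocular events*.
- Report two sub-rows, each with its own risk difference and 95% CI: (a) ocular events, meaning the three eye SMQs plus any terms for ocular manifestations found in the HLT on blinded review; (b) vitamin and laboratory terms, with vitamin A terms shown apart from other fat-soluble vitamins.
- Name the interval method in SAP 3.9.2.

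Keeping the HLT and sorting its terms avoids losing vitamin A disorders coded there. The cost is SAP wording, a blinded term review and extra table rows; no new data are needed.

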3.9.2.2 Other Adverse Events of Interest

The following list includes other adverse events that have been identified to be of interest:

Other AEs of interest	Definition
Coagulation abnormalities	AE with HLT: Coagulopathies
Abnormal liver function	AE within the SMQ: Drug related hepatic disorders – comprehensive search
Adverse events at the injection site	AE with HLT: Injection site reaction; or AE with HLT: Administration site reaction NEC
Flu-like symptoms	
 • AE with PT Influenza like illness; or • AE with PT Pyrexia (or Feeling hot or Body temperature increased) plus at least one of the following symptoms: 
 1. Chills 2. Myalgia 3. Arthralgia 4. Malaise 5. Fatigue 6. Headache 7. Nausea 
Note that only events that start on the day of the injection or the day after injection will be included. AEs with partial or missing dates will be handled as follows. First establish whether the event is treatment emergent. If yes, then establish if the preferred terms match the ones listed in the flu-like symptoms definition. If yes, check whether the event onset dates are within the specified time frame. If at this stage, onset date is missing or partially missing, the event will be considered to have started within the required time frame.

CNS disorders	AE with SOC: Nervous system disorders
Haemorrhages	AE within the SMQ: Haemorrhages
Complement activation	AE within SMQ: Hypersensitivity

Other AEs of interest	Definition
Reduced thyroxine	AE within SMQ: Hypothyroidism

For haemorrhages results will be further classified by type of event, using the following categories: actual bleeds, hematomas/subdermal bleeds, investigations SOC (test result), and DIC, TTP. Events classified as actual bleeds or hematomas/subdermal bleeds will be further categorized by whether the event occurred at injection site or not at injection site.

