2.3.3 Preclinical Experience

Detailed information concerning the preclinical studies conducted with ISIS 420915 can be found in the Investigator's Brochure. A summary is included below.

The nonclinical pharmacokinetics and toxicology evaluation of ISIS 420915 includes repeat dose studies up to 6 and 9 months in the CD-1 mouse and cynomolgus monkey, respectively. Nonclinical findings following ISIS 420915 treatment were, in general, non-specific class effects that are typical for 2'-MOE ASOs (Henry et al. 2008) and no findings were considered related to pharmacologic inhibition of TTR. Class effects occurred in a dose- and duration-dependent manner. In the monkey they included transient effects on acute complement activation (at doses ≥ 10 mg/kg/wk) and acute elevations in activated partial thromboplastin time (aPTT) (at doses ≥ 12 mg/kg/wk). The changes in aPTT were not cumulative over the course of the 9-month monkey study. In the mice, there was evidence of inflammation that included the presence of minimal to moderate mononuclear cell infiltrates in the sinusoids of liver, lymph nodes and the subcutaneous injection site at doses ≥ 40 mg/kg/wk after 3 and 6 months of treatment. Nonclinical pharmacokinetics (PK) of ISIS 420915 was similar to other second-generation ASOs. The exposure of ISIS 420915 in plasma and tissue was dose-dependent. The majority of ISIS 420915 was cleared from plasma within hours due mainly to distribution to tissues, with

kidneys and liver having the highest concentrations. The half-life in kidney and liver was approximately 13.5 days and 18.8 days, respectively, consistent with the plasma terminal elimination half-life of 17.0 days (at 8 mg/kg) after 4 doses.

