8.6.3 Stopping Rule for Platelet Count Results

In the event of a confirmed platelet count less than 75,000/mm³, and in the presence of major bleeding or clinically-relevant non-major bleeding (defined below; Schulman et al. 2005), dosing of a patient with Study Drug (ISIS 420915 or placebo) will be stopped permanently. The follow-up schedule for any events meeting this stopping criterion will be determined by the Investigator in consultation with the Study Medical Monitor.

In the event of a confirmed platelet count less than 75,000/mm³, and in the absence of major bleeding or clinically-relevant non-major bleeding, further dosing of a patient with Study Drug (ISIS 420915 or placebo) must be held until the platelet count returns to at least 100,000/mm³. Weekly platelet monitoring should continue during this period. In addition, the Investigator should give consideration to collecting duplicate platelet samples for study in a local lab in parallel to the central lab if it would provide quicker access to the patients platelet count. If the platelet count was confirmed to be < 50,000/mm³, then monitoring should be increased to daily until two successive values show improvement. The Investigator must notify the Study Medical Monitor within 24 hours of any local lab platelet results that show a level < 50,000/mm³.

The suitability of the patient for continued dosing and the need for any modification to treatment schedule or dose (refer to Section 8.7) will be determined by the Investigator in consultation with the Study Medical Monitor and will be based on factors such as the original rate of decline in the patient's platelet count, whether any bleeding events were experienced by the patient, and the speed of recovery of platelet count upon holding of dosing.

Definition major bleeding events:

International Society on Thrombosis and Haemostasis (ISTH) Major Bleeding:

1. Fatal bleeding, and/or
2. Symptomatic bleeding in a critical area or organ, such as intracranial, intraspinal, intraocular, retroperitoneal, intraarticular or pericardial, or intramuscular with compartment syndrome, and/or
3. Bleeding causing a fall in hemoglobin level of 20 g/L (1.24 mmol/L) or more within 24 hours, or leading to transfusion of 2 or more units of whole blood or red cells

Definition clinically-relevant, non-major bleeding events:

1. Multiple-source bleeding
2. Spontaneous hematoma > 25 cm²
3. Excessive wound hematoma (not injection site related)

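### The coagulation AE category has no laboratory term, unlike thrombocytopenia, and the SAP does not say that the haemorrhage risk difference is also given for bleeds alone

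*SAP*

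**What the plan says.** SAP 3.9.2.2 lists the other adverse events of interest. Coagulation abnormalities are defined as "AE with HLT: Coagulopathies" and nothing else. Haemorrhages are defined as "AE within the SMQ: Haemorrhages", that is, the whole standardised MedDRA query. The results for that category are then to be divided by type into "actual bleeds, hematomas/subdermal bleeds, investigations SOC (test result), and DIC, TTP". Within the two bleeding types, events "will be further categorized by whether the event occurred at injection site or not at injection site".

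SAP 3.9.2.1 defines Thrombocytopenia with two high-level terms (HLTs), the disorder term and "AE with HLT: Platelet analyses". The ocular category in the same table also adds preferred terms for a decreased or abnormal vitamin A result.

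SAP 3.9.2 sets the inference: "Statistical comparison between treatment groups will be done for AEs of special interest and other AEs of interest". The measure is the risk difference, ISIS 420915 minus placebo, with a 95% CI. The section does not say whether this applies to the category totals only or also to the haemorrhage types.

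**The concern.** The coagulation effect that the documents report for this drug is a laboratory one. Protocol 2.3.3 describes acute aPTT elevation in the monkey as a class effect. Protocol 9.5.1 lets an investigator record a clinically significant laboratory result as an adverse event. For platelets and vitamin A the SAP evidently expects some events to be coded as test results, and it adds terms to catch them. For coagulation it adds none. If a prolonged aPTT, PT or INR is coded under a laboratory term, the one planned between-group comparison labelled as coagulation does not count it.

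For Haemorrhages the question is narrower. By the SAP's own types, the SMQ total contains test results and DIC/TTP alongside actual bleeds. The trial has had severe thrombocytopenia and a fatal intracranial bleed (Protocol, Amendment 9 rationale), so readers will look for an interval estimate for bleeding itself. The SAP does not commit to one.

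**Working it through.** The documents give no event rate, power or error rate for either category, so there is no stated figure to reproduce. The check is a comparison of definitions, followed by an illustration on assumed counts.

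**Definitions side by side**

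- Thrombocytopenia (SAP 3.9.2.1): disorder HLT or laboratory HLT.
- Ocular events related to vitamin A deficiency (SAP 3.9.2.1): an HLT for fat-soluble vitamin deficiencies, two preferred terms for the vitamin A result, and three SMQs.
- Coagulation abnormalities (SAP 3.9.2.2): disorder HLT only.
- Haemorrhages (SAP 3.9.2.2): SMQ total, with a descriptive split by type and injection site.

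**Where a coagulation laboratory effect would still be seen**

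- SAP 3.9.2: all treatment-emergent events by system organ class and preferred term, by arm.
- SAP 3.9.4: coagulation panel values, change and percent change by visit and arm, without statistical comparison, and a listing of values outside normal ranges.
- Protocol 10.5.2: number of patients with laboratory abnormalities, by arm.
- SAP 3.9.4.1 to 3.9.4.3: threshold counts are specified for hepatobiliary, platelet and renal parameters. INR appears only jointly with raised ALT or AST.
- Protocol Appendix A: PT, aPTT and INR are drawn pre-dose in all patients during treatment. Draws at 3 and 12 hours post-dose are scheduled only in the PK subgroup of about 20.

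The signal would be visible descriptively. What is missing is the between-group estimate for the category.

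**Illustration**

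Denominators are the planned 90 and 45 patients (SAP 1.1). All event counts are assumed. With p1 = a/90 and p0 = b/45:

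- RD = p1 − p0
- SE = √[p1(1 − p1)/90 + p0(1 − p0)/45]
- 95% CI = RD ± 1.96 × SE

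The SAP names no interval method. This is the unpooled Wald interval, which is rough at such small counts and gives a zero placebo count no variance.

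*Coagulation.* Assume 1 vs 0 patients meet the disorder term. Then add patients who have laboratory-coded events only:

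- none: 1/90 vs 0/45, RD 1.1 points (−1.1 to 3.3)
- 2 vs 0: 3/90 vs 0/45, RD 3.3 (−0.4 to 7.0)
- 5 vs 1: 6/90 vs 1/45, RD 4.4 (−2.3 to 11.2)
- 9 vs 1: 10/90 vs 1/45, RD 8.9 (1.1 to 16.7)

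Worked for the last row: 0.1111 − 0.0222 = 0.0889; SE = √(0.001097 + 0.000483) = 0.0398; 0.0889 ± 0.0779.

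*Haemorrhages.* Assume 18 vs 5 patients with actual bleeds or hematomas. Then add patients who have only test-result or DIC/TTP events:

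- none: 18/90 vs 5/45, RD 8.9 (−3.5 to 21.2)
- 2 vs 2: 20/90 vs 7/45, RD 6.7 (−7.0 to 20.3)
- 5 vs 1: 23/90 vs 6/45, RD 12.2 (−1.2 to 25.6)

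The total can lie above or below the bleeds-only difference. If non-bleed events hit the same fraction q of patients in both arms, independently of bleeding, the total's difference is (1 − q) times the bleeds-only difference. At q = 5% it shrinks by only 5%. The mixture matters mainly when the non-bleed events differ by arm.

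**The case against.** Four points on the other side carry weight.

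*The coding is not in the documents.* Neither document says which preferred terms sit under HLT Coagulopathies. That a prolonged aPTT falls outside it is inferred from how Thrombocytopenia is built. This stands, and it is why the placement must be confirmed.

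*Few such events may occur.* Protocol 2.3.3 reports the monkey aPTT changes as acute, at 12 mg/kg/wk or more, and not cumulative over nine months. Most coagulation samples here are pre-dose. Protocol 9.5.1 prefers a diagnosis to a laboratory value and bars results judged not clinically significant. This also stands, and it keeps the size open down to zero.

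*Nothing is hidden.* A reader might infer that a laboratory-only effect would be reported as no coagulation effect. The preferred-term tables and laboratory summaries listed above contradict that. A reader might also infer that the same events would reappear as an excess of haemorrhage. The documents show that the SMQ holds some test-result terms, but not that these are coagulation tests.

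*Haemorrhages is labelled for what it is.* A reader might infer that this row misstates bleeding. It carries the SMQ's name, and the SAP already separates bleeds, hematomas, test results and DIC/TTP, and splits the bleeding types by injection site. The inference is not supported. What remains is that the SAP is silent on whether the risk difference follows that split.

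A reader might also ask for a row on major or clinically relevant non-major bleeding. Protocol 8.6.3 applies those definitions to a confirmed platelet count below 75,000/mm³ ("in the presence of major bleeding or clinically-relevant non-major bleeding"), so the documents do not show sites classifying every bleed this way. The row would need new classification work. Serious bleeds already reach the SAE and maximum-severity tables (SAP 3.9.2), and SAE narratives are planned (Protocol 10.5.2). That row is not part of this point.

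**Conclusion.** The coagulation definition is incomplete by the SAP's own standard for thrombocytopenia. On its face, the planned risk difference would omit adverse events coded only as coagulation test results. This assumes that such events code outside HLT Coagulopathies.

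For Haemorrhages the finding is limited to an unstated scope: the SAP should say whether the risk difference and CI are also given for bleeds alone.

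The size of either effect cannot be known from the documents. The ranges above (1.1 to 8.9 points for coagulation; 6.7 to 12.2 against 8.9 for haemorrhage) rest wholly on assumed counts, and neither estimate changes if no such events occur. Both categories are safety summaries outside the ordered tests of the two primary endpoints, so the primary inference is unaffected. The coagulation change is worth making because it is specific and nearly free. The haemorrhage change is a clarification.

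**What to change.** Make two edits before unblinding, the point by which SAP 2.6 requires the SAP to be final. Made later, a redefinition of safety categories could look data-driven.

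1. In SAP 3.9.2.2, define Coagulation abnormalities as HLT Coagulopathies or the HLT that holds coagulation laboratory analyses. Take the exact term from the MedDRA version used, and confirm there where prolonged aPTT, PT and INR are placed.
2. In SAP 3.9.2 or 3.9.2.2, state that the haemorrhage risk difference and 95% CI are given for the SMQ total and also for actual bleeds plus hematomas/subdermal bleeds combined, with and without injection-site events.

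The cost is a few lines of SAP text and a few extra table rows. The second edit reuses the type and injection-site classification already planned, so no new data or review of events is needed.
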